#### Erythema assessment

The assessing physicians will receive a specific training on how to assess dermatologic toxicity before study start. In case of no concordance between the two treating physicians in assessing toxicity, a third physician will be asked to evaluate the patient, and the toxicity grade receiving more agreement will be considered. Erythema assessment will be performed at each visit.

#### Spettrophotometry examination and TEWL examination

Objective in vivo measurements of skin erythema and pigmentation based on reflectance spectrometry (RS) will be performed. Skin reflectance measurements will be acquired in vivo by a spectrophotometric imaging system (SkinColorCatch, by Delfin Technologies Ltd. – Finland). At the clinical site, the Medical Physics Unit has a long tradition with spectrophotometric analysis, having developed a tool for automated melanoma detection and for the description of the blood and melanin content of pigmented skin lesions.

Measurements will be performed before RT start and then once a week at each visit before RT session and on clean skin. Instrumental RS measurements will be performed at three different fixed regions within the area treated with RT, in any case only on flat skin regions and in absence of hair or nevus. A control measurement will be done also in a specific contralateral area.

The trans-epidermal water loss (TEWL) exam will be done at the same time-points as for the spettrophotometry exam, before RT sessions. The exam will be conducted with VapoMeter instrument (Delfin Technologies Ltd. – Finland).

Measurements will be performed before RT start and then once a week at each visit, before RT session and on clean skin. Instrumental TEWL measurements will be performed at five different fixed regions within the area treated with RT, in any case only on flat skin regions and in absence of hair or nevus. A control measurement will be done also in a specific contralateral area.

#### Skindex-16 questionnaire

The Skindex-16 scale is a self-administered questionnaire to comprehensively measure the complex effects of skin diseases on subject's quality of life. The Skindex-16 measure is considered appropriate for a study since it has been shown to be reliable and valid for general skin disease.

The Skindex-16 allows patient rating of emotional and functional burdens that the CTCAE does not take into account. These adverse events cause patient's discomfort and impact negatively on quality of life.

The Skindex-16 questionnaire will be completed by the subject at each visit.

#### Patient Global Satisfaction

Global satisfaction evaluation by the subject will be assessed through a 5-point Likert scale (very poor, poor, medium, good, very good) at the end of the radiotherapy sessions and two weeks after the last irradiation.

Relevant variables will be derived for statistical analysis. Derived datasets will include the variables needed for any type of statistical analysis. The derived datasets will include all enrolled subjects. Flags will identify the populations to be analyzed, in order to select the subjects to be included in each statistical analysis (e.g. ITTLF = Y for ITT population).

#### **9.1.1 Baseline Values**

Baseline characteristics will be summarized using mean, median, standard deviation, minimum and maximum for continuous variables and frequencies and percentages for categorical variables.

#### **9.1.2 Duration of Exposure**

Duration of exposure will be estimated as the number of day under treatment, calculated using the following formula:

$$\text{Last day of treatment} - \text{first day of treatment} + 1$$

#### **9.1.3 Treatment Compliance**

The compliance with the treatment will be assessed through a diary where the patient will record the daily product applications and through the difference in weight of tubes when delivered to patient and when returned by the patient. The consistency between the two assessments will be checked (see paragraph 11.3).

#### **9.1.4 Methods for Withdrawals and Missing Data**

The number of patients withdrawn due to AE will be summarized by treatment arm.

Missing values will not be replaced unless specified otherwise. Missing safety data will not be replaced.

### **9.2 Multicenter Studies Considerations**

Not applicable.

### **9.3 Multiple Comparisons and Multiplicity**

No correction for multiplicity is needed, as the study has only a primary endpoint and the secondary endpoints have exploratory purposes. In case of clinically and statistically significant results, the exact p-value will be reported to support the strength of the findings.

#### 9.4 Data Safety Monitoring Board (DSMB)

Not applicable

### 10. STUDY SUBJECTS

In this clinical investigation 80 subjects will be enrolled: 40 of them will be female affected by breast cancer and 40 will be male and female affected by head & neck cancer, undergoing to postoperative or curative radiation treatment. All the subjects will be randomized to Xonrid® + SOC or SOC alone, only if they fulfill the following eligibility criteria:

#### Inclusion criteria

1. Male and female which are 18 years of age or older
2. Performance status < 2
3. Epithelial carcinoma of oropharynx, nasopharynx, larynx, hypopharynx, paranasal sinus and salivary glands or breast cancer, planned to receive a total dose of at least 50 Gy
4. Postoperative or curative radiation treatment
5. Concurrent chemotherapy is accepted, in head & neck cancer patients
6. Patients willing and able to give signed informed consent and, in the opinion of the Investigator, to comply with the Clinical Investigation Plan tests and procedures.

#### Exclusion criteria

7. Pregnant or lactating women
8. Planned to receive concurrent cetuximab
9. Previous radiation therapy on the head and neck area or breast and thorax areas
10. Cutaneous and connective diseases (i.e. lupus erythematosus or scleroderma)
11. Systemic diseases known to delay the skin healing process such as diabetes mellitus or severe renal failure
12. Use of a tissue-equivalent bolus
13. Use of over-the-counter topical medications containing steroids
14. Presence of rashes or unhealed wounds in the radiation field
15. Recent sun exposure

Should G3 skin toxicity develop, then, in any case, the study will be interrupted and the subject will be treated according to the Investigator's opinion.

### **10.1 Disposition of Subjects**

The disposition of subjects at each visit will be summarized.

### **10.2 Protocol Deviations**

The Investigator is to conduct the study in accordance with the relevant, current clinical investigation plan and will only deviate when necessary to protect the safety, rights and welfare of the subjects. In the event that an isolated, unforeseen instance occurs resulting in a clinical investigation plan deviation, the Investigator is to document this deviation and notify the CRO as soon as possible. In no instance should this increase the subject's risk or affect the validity of the study.

Protocol deviations will be reported. Protocol deviations will be examined and patients with critical deviations will be excluded from the analysis.

The Listing of protocol deviations will be reported in Appendix VI.2 of the Clinical Investigation Report.

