#### 4.3 Randomization and Blinding

The study was open label. Each patient for whom written consent was obtained have been assigned a five-digit screening code, consisting of the cancer area (e.g. 01 = head & neck; 02= breast) and a progressive number within the site: for example the first subject screened for head & neck cancer was assigned the code 01-001, the second one 01-002 etc.; the first subject screened for breast cancer was assigned the code 02-001, the second one 02-002 etc.

All screened subjects received the code irrespective of whether or not they were randomized. If a subject discontinued from the study at any time, the code was not re-used.

All subjects who signed the informed consent and received the screening code was entered into a Subject's Register, containing the name and surname of the patients and the date they have signed the consent form.

Eligible patients were randomized to receive the treatment according to a randomization list.

The patient randomization list was generated by Latis S.r.l., using the PROC PLAN of SAS 9.4 for Windows (SAS Institute Inc., Cary, NC, USA). Once eligibility of a patient was established (see Inclusion/Exclusion Criteria) the study treatment was assigned through centralized randomization system.

The Investigator also kept record of all enrolled patients in the Subject's Enrolment Log: the subject screening number, the date of consent, the treatment assigned to the patient, if applicable, or the reason for not being randomized were recorded.

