## 8. ANALYSIS POPULATIONS

### 8.1 Intent-to-Treat Population (ITT)

The study will be analyzed using an Intent-to-Treat (ITT) approach. All randomized patients receiving at least a treatment dose and having at least one post-randomization efficacy evaluation will be included in the ITT population for efficacy analysis. All randomized patients receiving at least a treatment dose will be included in the safety analysis.

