### 8.2 Per-Protocol (PP) Population

Not applicable.

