### 8.3 Safety Population

All randomized patients receiving at least a treatment dose will be included in the safety population.

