## **11. EFFICACY ANALYSIS**

### **11.1 Analysis datasets**

The study will be analyzed using an Intent-to-Treat (ITT) approach. All randomized patients receiving at least a treatment dose and having at least one post-randomization efficacy evaluation will be included in the ITT population for efficacy analysis. All randomized patients receiving at least a treatment dose will be included in the safety analysis.

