## 11.5 Summary of Efficacy Analyses

Endpoint	Analysis	Populations
Proportion of patients without G2 radiation dermatitis at week 5	The proportion of patients without G2 radiation dermatitis (radiation dermatitis < G2) at week 5 will be assessed and compared between treatment groups using chi-square test. Logistic regression will be performed to obtain Odds Ratio.	ITT
Median time to G2 radiation dermatitis development according to CTCAE	Median time to G2 radiation dermatitis will be analyzed using Kaplan-Meier method and compared between treatment groups using log-rank test.	ITT
Proportion of patients without G2 radiation dermatitis at week 6 for both cancer sites, at week 7 for head & neck cancer and 2 weeks after the last radiation for both cancer sites	The proportion of patients without G2 radiation dermatitis at week 6 for both cancer sites, at week 7 for head & neck cancer and 2 weeks after the last radiation for both cancer sites will be assessed and compared between treatment groups using chi-	ITT

weeks after the last radiation for both cancer sites.	square test. Logistic regression will be performed to obtain Odds Ratios	
Changes in skin erythema and pigmentation and trans-epidermal water loss (TEWL)	The changes in skin erythema and pigmentation and in trans-epidermal water loss (TEWL) will be graphically described throughout the study. Changes between before the first RT session and the end of RT and between the end of RT and the end of treatment will be analyzed and compared between treatment groups using ANCOVA, to adjust the estimates for baseline values.	ITT
Mean and worst score of Patient Reported Outcome (PRO) with Skindex-16 questionnaire performed weekly	Weekly mean and worst score of Skindex-16 questionnaire will be compared between treatment groups using ANCOVA, to adjust the estimates for baseline values.	ITT
Compliance to experimental treatment use	The compliance with the treatment will be assessed through a diary where the patient will record the daily product applications and through the difference in weight of tubes when delivered to patient and when returned by the patient. The consistency between the two assessments will be checked.	ITT
Patient global satisfaction with treatment as assessed by Likert scale	The patients' global satisfaction with treatment, assessed by Likert scale, will be compared between treatment groups using Kruskal-Wallis test.	ITT

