## 13. DEVIATIONS FROM THE PROTOCOL SPECIFIED ANALYSIS

The worst skin toxicity during treatment and until 2 weeks after the last radiation will not be analyzed, as most of the patients reached G2 skin toxicity.

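### SAP 10.2 removes patients with undefined critical deviations from the analysis, which contradicts the ITT set assigned to the primary endpoint

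*SAP*

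**What the plan says.** The section on protocol deviations (SAP 10.2) ends with an exclusion rule: "Protocol deviations will be examined and patients with critical deviations will be excluded from the analysis".

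The population sections say otherwise. SAP 8.1: "The study will be analyzed using an Intent-to-Treat (ITT) approach". SAP 11.1, which follows directly after 10.2: "All randomized patients receiving at least a treatment dose and having at least one post-randomization efficacy evaluation will be included in the ITT population". Protocol 7.2 gives the same definition. The entry for a per-protocol population (SAP 8.2) reads "Not applicable". The safety set (SAP 8.3) is equally free of any deviation criterion: "All randomized patients receiving at least a treatment dose will be included in the safety population".

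SAP 11.5 lists ITT as the population for the primary endpoint, "Proportion of patients without G2 radiation dermatitis at week 5", and for every other efficacy endpoint it retains. Protocol section 10 asks only that deviations be documented and notified to the CRO. SAP 13, the place for declaring departures from the protocol's analysis, does not mention the exclusion rule.

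**The concern.** For a patient who was dosed and evaluated but has a critical deviation, the programmer cannot obey both 10.2 and 11.1. No per-protocol set exists to which the exclusion could belong, and the protocol contains no such rule.

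The rule is also open-ended. *Critical* is not defined, no decision-maker or time point is named, and *the analysis* is unqualified, so read literally it could reach the safety set too. SAP 4.3 says "The study was open label", so whoever classifies a deviation can know the arm. SAP 13 drops worst skin toxicity, which "will not be analyzed, as most of the patients reached G2 skin toxicity"; overall toxicity results were therefore known when the SAP was written. This does not show that results by arm had been seen or that anyone misused the rule. It shows that nothing in the plan shields an exclusion from knowledge of arm and outcome.

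At stake is the primary comparison: randomised patients could be removed on criteria not fixed in advance while the result is still labelled ITT. The bias could go either way. Deviations can occur in both arms, but missed applications of dispensed gel arise only in Group A.

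**Working it through.** **1. Passages side by side, for a randomised, dosed, evaluated patient with a critical deviation**

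| Source | Treatment of this patient |
|---|---|
| Protocol 7.2; SAP 8.1, 11.1 | In the ITT set for efficacy |
| SAP 11.5 | Analysed for each retained efficacy endpoint |
| SAP 8.2 | No per-protocol set available |
| SAP 8.3 | In the safety set (dosing suffices) |
| SAP 10.2 | Excluded from the analysis |

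The last row conflicts with the others.

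**2. The plan's own sample size.** Inputs from protocol 7.1: 38.2% v 82.9% without G2 at week 5, two-sided 0.05, 80% power. The mean rate is 0.6055.

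n = [1.96√(2 × 0.6055 × 0.3945) + 0.8416√(0.382 × 0.618 + 0.829 × 0.171)]² / 0.447² = 17.5, so 18 per group; 18/0.9 = 20 with dropout.

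Both stated figures reproduce, and the sample size is not in dispute. Because SAP 9.1 analyses each cancer site separately, each comparison has up to 20 per arm. Approximate power is 85.3% at 20 per arm and 81.1% at 18. If exclusions came on top of the planned dropout, it would be 78.7% at 17, 76.0% at 16 and 73.0% at 15.

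**3. Effect of one exclusion.** The documents give no deviation counts, so these tables are assumed. Pearson chi-square without continuity correction, with p̄ the pooled proportion:

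X² = (a/n − b/m)² / [p̄(1 − p̄)(1/n + 1/m)]

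First row: 0.30² / (0.25 × 0.10) = 3.60.

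| Group A v Group B without G2 | p | After dropping one Group A patient | p |
|---|---|---|---|
| 13/20 v 7/20 | 0.058 | 13/19 v 7/20 (a failure dropped) | 0.037 |
| 16/20 v 10/20 | 0.047 | 15/19 v 10/20 (a success dropped) | 0.060 |
| 17/20 v 8/20 | 0.003 | 17/19 v 8/20 (a failure dropped) | 0.001 |

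The first row gains significance, the second loses it, and the third, near the planned effect, does not change.

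**4. How often a result is that fragile.** Sum the binomial probabilities of all 20 v 20 tables in which a single exclusion changes whether p<0.05. Two versions are shown: at least one possible exclusion does so (upper bound), and one patient drawn at random from the 40 does so.

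| True rates, A v B | Some exclusion changes the result | Random exclusion changes it |
|---|---|---|
| 82.9% v 38.2% (planned) | 9.3% | 3.2% |
| 65% v 35% (assumed) | 13.7% | 4.9% |
| 38.2% in both (no effect) | 6% | 1.8% |

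**5. Selective exclusion under no effect (worst case).** Removing three G2 patients from one arm only raises the exact size of the test from 5.0% to 8.1% at a common rate of 38.2%, and from 4.8% to 12.4% at an assumed common rate of 60%.

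**The case against.** Five points can be made for the plan.

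- *The passages might be compatible.* The ITT set already requires a dose and an evaluation. If *critical* meant only deviations that leave a patient without one of these, 10.2 would add nothing. The SAP does not say so, and the ordinary meaning is wider.
- *Exclusions would be visible.* Listing VI.3 covers patients excluded from the efficacy analysis, and SAP 9.1 keeps all enrolled subjects in the derived datasets with population flags. The full ITT result could therefore be recovered. This limits the harm, but VI.3 gives no criteria, may simply list those who fail the ITT definition, and does not say which result is primary. It does suggest that efficacy is the intended target, so the reach into the safety set is only a possible literal reading.
- *The fragility figures are upper bounds.* This is correct: they assume the most influential patient is the one removed. The random-exclusion figures are about a third as large, and actual impact could be nil.
- *Outcome knowledge is pooled.* This is also correct: SAP 13 reveals nothing by arm, and the final analysis follows database lock. The concern about knowing the arm rests on the open-label design.
- *Gel deviations are not strictly confined to Group A.* The product is commercially available, so a Group B patient could use it. Only missed applications of dispensed gel are specific to Group A.

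These points narrow the likely size of the problem but leave the contradiction in place.

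**Conclusion.** The concern holds and must be fixed. As written, the SAP leaves the population of the primary comparison indeterminate: 10.2 excludes patients whom protocol 7.2 and SAP 8.1 and 11.1 include, under an undefined term, and the departure from the protocol is not declared in SAP 13. This is an error in the text, beyond missing detail.

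The actual size is unknown because no deviation counts are given. At about 20 per arm and site, a single exclusion can move a borderline result in either direction; a result near the planned effect is robust in the example shown. The contradiction itself follows from the text and depends on none of the assumed counts.

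**What to change.** In SAP 10.2, delete the part of the sentence that excludes patients with critical deviations, and add:

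*No patient who meets the ITT definition in 8.1 or the safety definition in 8.3 is excluded because of a protocol deviation; deviations are listed in Appendix VI.2.*

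State that ITT patients are analysed in the arm assigned, and that listing VI.3 shows only patients who fail the 8.1 criteria. If an analysis without major deviators is wanted, define those deviations before any output by arm is produced, declare the analysis in SAP 13 and label it a sensitivity analysis beside the primary ITT result.

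The cost is SAP wording only: no protocol amendment and no new data. The one drawback is that the ITT estimate may be somewhat diluted by non-adherent patients.

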## **11. EFFICACY ANALYSIS**

### **11.1 Analysis datasets**

The study will be analyzed using an Intent-to-Treat (ITT) approach. All randomized patients receiving at least a treatment dose and having at least one post-randomization efficacy evaluation will be included in the ITT population for efficacy analysis. All randomized patients receiving at least a treatment dose will be included in the safety analysis.

### **11.2 Demographics and Baseline Characteristics**

Demographic (gender, age) and baseline characteristics will be summarized using mean, median, standard deviation, minimum and maximum for continuous variables and frequencies and percentages for categorical variables. To compare demographic and baseline characteristics between treatment groups, chi-square or t-tests will be used for discrete and continuous variable, respectively.

### **11.3 Measurements of Treatment Compliance**

Compliance to the treatment will be assessed through the number of applications performed by the patients, as reported on patient's diary. As three applications a day were planned, the effective number of days of treatment will

be multiplied by three, to obtain the number of planned applications. The number of applications reported during the treatment period will be compared with the number of planned applications to obtain the compliance percentage.

$$\text{Compliance \%} = \frac{\text{Number of applications reported}}{\text{Number of applications planned}} \times 100$$

The bottles have been weighted before treatment and after treatment, as returned by the patients. The amount of product used will be estimated as the difference between the bottle weight before treatment and the weight of the same bottle after treatment.

The number of applications reported will be compared with the weight of product used using linear regression.

## 11.4 Efficacy Analysis

### 11.4.1 Primary Efficacy Endpoints

The primary objective of this clinical investigation is to evaluate the proportion of patients without G2 radiation dermatitis (radiation dermatitis < G2) at week 5. The proportion of subjects will be compared between treatment groups using chi-square test. The following SAS code will be used for chi-square test:

```
proc freq;
table treatment * patient_G2_yn / CHISQ;
run;
```

Logistic regression will be used to obtain Odds Ratio (OR), with 95% Confidence Interval (95% CI). No adjustment for covariates will be performed.

The following SAS code will be used for logistic regression:

```
proc logistic;
class treatment;
model depvar = trtan / expb;
run;
```

### 11.4.2 Secondary Efficacy Endpoints

The median time to G2 radiation dermatitis development will be analyzed using Kaplan-Meier method.

Comparisons between treatment groups will be performed using log-rank test.

```
proc lifetest;
time time_to_G2 * G2_yn(0);
strata treatment / test=( logrank );
test treatment;
run;
```

The proportion of patients without G2 radiation dermatitis at week 6 for both cancer sites, at week 7 for head & neck cancer and 2 weeks after the last radiation for both cancer sites will be assessed and compared between treatment groups using chi-square test. Logistic regression will be used to obtain ORs, with 95% CIs, and to eventually adjust for covariates. The same method used for primary objective will be applied.

The changes in skin erythema and pigmentation will be graphically described reporting the ITA (individual Typological Angle) degrees throughout the study. The ITA of the area treated with RT will be obtained averaging the ITA measured at the three different fixed regions, adjusted for the control measurement done in a specific contralateral area. Changes between visit 2, before the first RT session, and the end of RT and between the end of RT and the end of treatment will be analyzed and compared between treatment groups using ANCOVA, to adjust the estimates for baseline values.

The following SAS code will be used for ANCOVA analysis:

```
proc glm;
  class treatment;
  model avg_ITA = treatment avg_ITA_baseline;
  run;
```

where avg\_ITA at each timepoint and avg\_ITA\_baseline have been obtained as follows:

```
ITA_diff1 = ita_rt1 - ita_controlateral;
ITA_diff2 = ita_rt2 - ita_controlateral;
ITA_diff3 = ita_rt3 - ita_controlateral;
avg_ITA#= mean(ITA_diff1, ITA_diff2, ITA_diff3, ITA_diff4, ITA_diff5);
```

The changes in trans-epidermal water loss (TEWL) will be graphically described reporting the Evaporation rate value (ERV, measured in g/m^2h) throughout the study. The ERV of the area treated with RT will be obtained averaging the ERV measured at the five different fixed regions, adjusted for the control measurement done in a specific contralateral area. Changes between visit 2, before the first RT session, and the end of RT and between the end of RT and the end of treatment will be analyzed and compared between treatment groups using ANCOVA, to adjust the estimates for baseline values.

The following SAS code will be used for ANCOVA analysis:

```
proc glm;
  class treatment;
  model avg_TEWL = treatment avg_TEWL_baseline;
  run;
```

where avg\_TEWL and avg\_TEWL\_baseline have been obtained as follows:

```
TEWL_diff1 = tewl_rt1 - tewl_ct;
TEWL_diff2 = tewl_rt2 - tewl_ct;
```

```

TEWL_diff3 = tewl_rt3 - tewl_ct;
TEWL_diff4 = tewl_rt4 - tewl_ct;
TEWL_diff5 = tewl_rt5 - tewl_ct;
avg_TEWL #= mean(TEWL_diff1,TEWL_diff2,TEWL_diff3,TEWL_diff4,TEWL_diff5);

```

The mean and worst score of Skindex-16 questionnaire will be compared between treatment groups using ANCOVA, to adjust the estimates for baseline values.

The following SAS code will be used for ANCOVA analysis:

```

proc glm data = DB;
class treatment;
model skindex_score = treatment skindex_score_b1 ;
run;

```

Both the number of daily product applications reported on the patient's diary and the amount of used product, estimated through the difference in tubes weight between delivery to patient and return, will be used to assess the compliance to experimental treatment. The consistency between the two assessments will be checked through linear regression.

The patients' global satisfaction with treatment, assessed by Likert scale, will be compared between treatment groups using Kruskal-Wallis test.

```

proc npar1way;
class TREATMENT;
var satisfaction;
run;

```

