7.3.3 Covariates, Interactions and Subgroups

Due to the limited number of patients to be enrolled, covariates and subgroup analyses, if any, will be performed only with exploratory purposes.

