7.3.5.2 Secondary endpoints

The median time to G2 radiation dermatitis development will be analyzed using Kaplan-Meier method. Comparisons between treatment groups will be performed using log-rank test.

The proportion of patients without G2 radiation dermatitis at week 6 for both cancer sites, at week 7 for head & neck cancer and 2 weeks after the last radiation for both cancer sites will be assessed and compared between treatment groups using chi-square test. Logistic regression will be used to obtain ORs, with 95% CIs, and to eventually adjust for covariates.

The worst skin toxicity during treatment and until 2 weeks after the last radiation will be compared between treatment groups using ANOVA.

The changes in skin erythema and pigmentation will be graphically described reporting the ITA (individual Typological Angle) degrees throughout the study. The ITA of the area treated with RT will be obtained averaging the ITA measured at the three different fixed regions, adjusted for the control measurement done in a specific contralateral area. Changes between visit 2, before the first RT session, and the end of RT and between the end of RT and the end of treatment will be analyzed and compared between treatment groups using ANCOVA, to adjust the estimates for baseline values.

The changes in trans-epidermal water loss (TEWL) will be graphically described reporting the Evaporation rate value (ERV, measured in g/m²h) throughout the study. The ERV of the area treated with RT will be obtained averaging the ERV measured at the five different fixed regions, adjusted for the control measurement done in a specific contralateral area. Changes between visit 2, before the first RT session, and the end of RT and between the end of RT and the end of treatment will be analyzed and compared between treatment groups using ANCOVA, to adjust the estimates for baseline values.

The mean and worst score of Skindex-16 questionnaire will be compared between treatment groups using ANCOVA, to adjust the estimates for baseline values.

Both the number of daily product applications reported on the patient's diary and the amount of used product, estimated through the difference in tubes weight between delivery to patient and return, will be used to assess the compliance to experimental treatment. The consistency between the two assessments will be checked through linear regression.

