## 9. GENERAL ISSUES FOR STATISTICAL ANALYSIS

### 9.1 Definitions, Derived Variables and Datasets

Analyses will be performed and report separately for each cancer site (i.e., breast cancer and head and neck cancer).

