## 14.4.3 Sample table for efficacy analysis – discrete variables

Sponsor: Helgina Healthcare SA  
Protocol HD01-16-30

Page 1 of x

Table xx.x.x.x  
Summary and Analysis of \_\_\_\_\_  
(\_\_\_\_\_ Population)

Characteristic	Statistic	ARM A (n=xxx)	ARM B (n=xxx)
Var1	Class A	xx ( xx,xx )	xx ( xx,xx )
	Class B	xx ( xx,xx )	xx ( xx,xx )
	p-value		xx,xxx**
Var2	Class A	xx ( xx,xx )	xx ( xx,xx )
	Class B	xx ( xx,xx )	xx ( xx,xx )
	p-value		xx,xxx**

Statistical significance: \* p<0.05; \*\* p<0.01667; \*\*\* p<0.01; \*\*\*\* p<0.001.  
Note: p-values from a chi-square test.

Program: xx.xxxxxxx xxz.dax

CONFIDENTIAL

Date: xx/xx/xxxx

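### Does SAP 11.4.2 leave open whether the secondary odds ratios are covariate-adjusted?

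*SAP*

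**What the plan says.** SAP 11.4.2 covers the proportion of patients without grade 2 dermatitis at week 6 (both sites), week 7 (head and neck) and two weeks after radiotherapy (both sites). Each is compared by chi-square test. Logistic regression then supplies odds ratios with 95% intervals "and to eventually adjust for covariates. The same method used for primary objective will be applied".

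The method referred to is in SAP 11.4.1, which states "No adjustment for covariates will be performed" and gives the model statement "model depvar = trtan / expb", with no term but treatment.

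The adjustment wording comes from protocol 7.3.5.2: "Logistic regression will be used to obtain ORs, with 95% CIs, and to eventually adjust for covariates". Protocol 7.3.5.1 had the same wording for the primary endpoint. The SAP replaced it there and kept it here. Protocol 7.3.3 limits all such work: "covariates and subgroup analyses, if any, will be performed only with exploratory purposes". The SAP 11.5 row for these endpoints says only "Logistic regression will be performed to obtain Odds Ratios".

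**The concern.** Two consecutive sentences appear to give different models. One keeps adjustment available. The next points to a method that rules it out. Neither document names a covariate, a condition for adjusting, or which odds ratio would be the one reported. On that view, two analysts could report different odds ratios and intervals for the same endpoint.

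The timing adds to the worry. The trial is open label. The SAP is dated 18 December 2018 and describes enrolment as complete. Its section 13 drops an endpoint because most patients had reached grade 2, so some outcome information was already known. An unnamed covariate set at that stage could in principle be filled in after looking at the data.

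A side issue is that both documents name concomitant chemotherapy as a driver of dermatitis, yet SAP 11.2 names only gender and age among the variables it will summarise.

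**Working it through.** **1. How many odds ratios are involved.** SAP 9.1 states "Analyses will be performed and report separately for each cancer site". Week 6 gives 2 (two sites), week 7 gives 1 (head and neck only), and two weeks after radiotherapy gives 2. Total 2 + 1 + 2 = 5. SAP 14.2 lists tables for four of them; it has none for head and neck at week 7.

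**2. What the SAP does when it means to adjust.**

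- ITA, TEWL and Skindex-16: 11.4.2 states baseline adjustment, the code carries the baseline term, and the 11.5 rows repeat it.
- Primary proportion: 11.4.1 rules adjustment out, and the code has treatment only.
- Later proportions: an optional clause, then a pointer to the primary method. There is no separate code, and 11.5 is silent on covariates.

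The third case matches the second, not the first. The sample table for discrete outcomes shows counts and carries the footnote "Note: p-values from a chi-square test". It shows no odds ratio, so it supports neither reading.

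**3. Size per site.** Inputs from SAP 7: 38.2% v 82.9%, two-sided 0.05, 80% power. The mean rate is (0.382 + 0.829)/2 = 0.6055.

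n = [1.960 × √(2 × 0.6055 × 0.3945) + 0.842 × √(0.382 × 0.618 + 0.829 × 0.171)]² / 0.447² = 17.5, so 18 per group.

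18/(1 − 0.10) = 20 per group. The plan's figures reproduce, and 20 per arm is used below.

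**4. What would change if someone adjusted.** The documents give no late grade-2-free rates, covariate shares or covariate effects, so every input here is assumed.

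- *The estimate.* At the planning rates the unadjusted odds ratio is (0.829/0.171)/(0.382/0.618) = 7.84. With one balanced binary covariate at 50% prevalence, the adjusted value for the same marginal rates would be 7.84, 8.28, 9.72 or 12.67 if the covariate's own odds ratio were 1, 2, 4 or 8.
- *The conclusion, with a treatment effect.* Simulated trials used 20 per arm, one binary covariate (share 30–70%, effect 0–20 percentage points), and true rates of 20% v 40%, 20% v 50% or 15% v 45%. The two models disagree on whether the 95% Wald interval excludes 1 in 3.2–8.3% of trials per odds ratio. The two odds ratios differ by a median factor of 1.05–1.13 (90th percentile 1.24–1.74). With 38.2% v 70% and a covariate odds ratio of 4, disagreement is about 10%. With three covariates at 20% v 50%, it is 8.8–10.9%.
- *The conclusion, with no treatment effect* (15% or 20% in both arms, one covariate). Disagreement is 0.4–1.6%.
- *Any of the five.* With disagreement d per odds ratio, use 1 − (1 − d)² if time points within a site move together and 1 − (1 − d)⁵ if all were independent. With an effect (d = 0.032 to 0.083): 6.3–15.9% and 15.0–35.2%. With no effect (d = 0.004 to 0.016): 0.8–3.2% and 2.0–7.7%. Full independence is unrealistic, since the same patients supply two or three time points per site.
- *What staying unadjusted gives up.* With one covariate, the share of intervals excluding 1 changes by −0.9 to +2.4 percentage points on adjusting. The −0.9 comes from one extreme scenario (15% v 45%, share 70%, effect 20 points) where a repeat gave +1.4, so its sign should not be read. Either way the loss is small.

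**The case for a change.** The best case for an edit is that the clause was removed for the primary endpoint and kept for the secondary ones, which could be deliberate. The pointer to the primary method could mean only chi-square plus logistic regression, with adjustment still available. The silence of 11.5 is not conclusive, because the protocol synopsis is equally silent while protocol 7.3.5.2 keeps the clause. Being exploratory lowers the stakes but does not fix the model, and in an open-label trial with outcomes partly known an open option is better closed. Deleting a few words would cost almost nothing.

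Part of this stands. The wording is untidy, and SAP 13 does not mention adjustment. But the clause is permissive. Running the unadjusted model satisfies it, so the two sentences can both be followed. An adjusted odds ratio, if one were added, would fall under protocol 7.3.3 and be exploratory. Nothing in either document proposes choosing among models, so worries about searching for a favourable covariate describe a hypothetical and not this plan.

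The chemotherapy point shows no omission. SAP 11.2 covers baseline characteristics without limiting them to gender and age, SAP 14.1 lists a separate table of disease details for head and neck patients, and concomitant therapies are recorded at every visit. A dedicated row would be a preference, and it would not bear on which logistic model is fitted.

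**Conclusion.** No change follows. SAP 11.4.2 carries a leftover optional clause, and an analyst following the section together with 11.4.1 and 11.5 will fit the treatment-only model. That yields valid unadjusted odds ratios for five endpoints that SAP 9.3 already calls exploratory. The week-5 primary analysis and every chi-square p-value are untouched.

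If the other reading were taken with one covariate, the two models would seldom disagree on whether the interval excludes 1: 3.2–8.3% of trials per odds ratio with a treatment effect, 0.4–1.6% without. Stronger or additional covariates push this to about 10%. These sizes depend entirely on assumed rates and covariates. The conclusion depends on reading the clause as optional, which its wording and protocol 7.3.3 both support.
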